The novel combination of existing lifestyle intervention components resulting from phase 1 of the research will subsequently be evaluated using a pragmatic randomized intervention design. The goal of this research is to evaluate the new cluster of interventions, which we call Coordinating Pragmatic Primary care Population management for Obesity (C3PO), among a sample of patients who are representative of all patients who might be offered the intervention in routine practice. Thus, instead of recruiting highly selected research volunteers for the pilot trial, we will use a pragmatic randomization design that will use a “behind the scenes” randomization approach to assign 80 eligible patients to receive Basic Resources and Services for healthy lifestyle support (n=40) or the C3PO pilot intervention (n=40). We will not collect data for research purposes only in this trial. Rather, we will use routinely collected clinical data (i.e. available from the electronic health record) for each patient. Following completion of the 4-month pilot trial phase, we will then recruit and consent 20 patients who were eligible for the intervention to complete semi-structured interviews to assess patient experiences, perceptions, and barriers faced during the intervention period. This final step will help to inform any additional relevant intervention refinements prior to conducting a larger and more definitive future trial of the intervention’s effectiveness.

Figure 1. Development & Pre-Testing of a Novel Intervention for Coordinating Pragmatic Primary care Population management for Obesity (C3PO)

THE INTERVENTION DEVELOPMENT PHASE HAS 4 GENERAL OBJECTIVES:

- 1) **ASSESS HEALTHCARE PROVIDER PERCEPTIONS REGARDING C3PO INTERVENTION NEEDS, PRIORITIES, AND PREFERENCES**
- 2) **ASSESS EXISTING RESOURCES & WORKFLOWS**
- 3) **INTEGRATE EXISTING WORKFORCE, WORKFLOW, AND IT COMPONENTS NEEDED FOR POPULATION HEALTH MANAGEMENT TO BE EFFICIENT AND EFFECTIVE**
- 4) **PRETEST IT COMPONENTS USING LIMITED PATIENT USABILITY TESTING**

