For Research Activity #1, this study will utilize the following information about clinical staff member participants (not PHI):

- *Names (first and last)*
- *Work telephone numbers, Email addresses*
- *Professional role (e.g. staff physician, PA, NP, RN, LPN, MA, care coordinator, clerk, etc)*
- *Sex/Gender*
- *Year completing training*
- *Year beginning current employment at NMG*
- *Attitudes and beliefs about role in patient weight management support and use of health IT to achieve this*

For Research Activities #2 & 4, this study will utilize the following information about patient participant, collected directly from the participant or from administrative and clinical data systems during routine care delivery and queried at the individual level via the Northwestern Medicine Enterprise Data Warehouse (includes (includes PHI):

- *Names (first and last)*
- *Elements of patient's address including street address, city, county, ZIP code*
- *Telephone numbers, Email addresses*
- *Age*
- *Sex/Gender*
- *Race/Ethnicity*
- *Primary or preferred language*
- *MyChart Status (Active vs. Not Active)*
- *Body Weight measured at the last clinical patient visit*
- *Cardiovascular risk factors (High Blood Pressure; dyslipidemia; diabetes; prediabetes) indicated in the EPIC active patient problem list*
- *Healthy lifestyle goals*
- *Video and audio recordings of the patient during use of MyChart and a wireless home scale (Research Activity #2)*
- *Perceptions of healthy behavioral clinical services and support tools, including perceived benefits, barriers, and suggestions for improvements (Research Activities #2 and #4)*

For Research Activity #3 (trial with waiver of HIPAA authorization), this study will utilize the following information about patient participants, all collected from administrative and clinical data systems during routine

STU#: STU00207153

care delivery and queried at the individual level via the Northwestern Medicine Enterprise Data Warehouse (includes (includes PHI):

- Age
- Sex/Gender
- Race/Ethnicity
- Primary or preferred language
- Body Weight and Height measured at clinical patient visits during the follow up period
- Cardiovascular risk factors (High Blood Pressure; dyslipidemia; diabetes; prediabetes) indicated in the EPIC active patient problem list
- A1C and glucose values measured at clinical patient visits during the follow up period
- Systolic blood pressure measured at clinical patient visits during the follow up period

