We assessed the feasible capture of body weight measures from two pragmatic data sources: electronic health records and cellular-enabled, wireless body weight scales (eScales), which were provided to all participants at the time of randomization. We extracted the date and value of all body weight recordings in the electronic health record of each eligible patient participant during the 12 months before his/her study randomization date (each occurred between 12/16/2019 and 1/6/2020). We also extracted the date and value for all body weight measures available from either the electronic health record or from eScale transmissions during the 15-month period after each individual's study randomization. The last electronic health record weight measure prior to the randomization date served as the baseline body weight for constructing the primary weight change outcome variable. The electronic health record weight measure closest to the date of randomization plus 180 days (6 months) was selected for the follow up body weight measure for the primary outcome analysis. For patients who did not have a follow up weight value in the electronic health record between 6 months +/- 3 months, we searched the electronic health record for a weight value between 12 months +/- 3 months. For participants missing 6-month weight values, we imputed their 6-month value as equal to one half the distance between the baseline and 12 month value. For participants missing both a 6- and 12-month weight value in the electronic health record, we used the eScale weight value closest to 6 months +/- 3 months. Finally, if individuals were missing all of these weight values, we assumed conservatively for the primary outcome analysis that the participant failed to reach the 5% weight loss threshold. All blood pressure, A1c, and cholesterol test results were extracted similarly from the electronic health record. As this was a small pilot trial, when analyzing mean change at different time points, we analyzed only those patients with available outcome measures and did not use advanced imputation approaches for replacing missing values.

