**Statistical Analysis:** We examined univariate and bivariate descriptive statistics and conducted chi-square or Fisher exact tests to compare all patients randomized to intervention and control arms on the proportion that reached the dichotomous primary outcome of clinically meaningful weight loss at 6 months. We conducted t-tests to compare all patients with available outcome measures in each study arm with respect to all pre-specified, continuous outcomes (e.g., mean changes in body weight, systolic blood pressure, hemoglobin A1c, total cholesterol, and non-HDL cholesterol). Multivariate models (ANCOVA and multivariate logistic regression) were used to estimate adjusted means (continuous variables) or proportions (categorical variables) for each pre-specified outcome. We explored stratified analyses by age and by sex to understand if preliminary outcome differences appeared to vary with these biologic variables.

Input from health system leaders and study team members were used to identify the principal "ingredients" of study interventions. Inputs included personnel, supplies, contract services, and facility and administrative costs, all from the perspective of the health system. Administrative data on the number and type of contacts made between nurses and study participants, as well as interviews with staff to identify time spent in other activities was used to estimate %FTE spent with patients in each study arm over 6 and 12 months. Costs of eScales and community intervention program fees were estimated from the invoice amounts to estimate cost per person and overall. One-time development or startup costs for health IT was estimated from contract amounts and invoiced payments for work performed. Operational or maintenance costs for IT support was estimated from interviews of IT staff members, who were asked to estimate hours per week spent supporting the intervention components. Research-only costs were excluded from intervention cost estimations. Since many health payers currently reimburse for lifestyle interventions costing between \$400 and \$800 per person annually, preliminary estimates for intervention costs equal or less than this were considered supportive of health system sustainability and were used as a threshold for proceeding to a larger future trial that will include a more intensive net cost and cost-effectiveness analysis.

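### Mean changes in weight and risk factors are compared only among patients with a recorded value, so the pilot's preliminary effect sizes could be biased if availability works differently in the two arms

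*SAP*

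**What the plan says.** The SAP (Analysis Plan, Data Sources & Collection) states the rule for mean change at each time point: "we analyzed only those patients with available outcome measures and did not use advanced imputation approaches for replacing missing values". The reason it offers is that this is a small pilot. Its Statistical Analysis paragraph uses the same set for testing: "We conducted t-tests to compare all patients with available outcome measures in each study arm". The outcomes listed are body weight, systolic blood pressure, A1c, total cholesterol and non-HDL cholesterol. It adds that "Multivariate models (ANCOVA and multivariate logistic regression) were used to estimate adjusted means", but names no covariates and no other handling of missing values. No sensitivity analysis is described for these outcomes, and no comparison of patients with and without a value.

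On where values come from, the Protocol (Phase 2: Intervention Evaluation) says "We will not collect data for research purposes only in this trial". Its list of trial data (Protected Health Information) includes "Body Weight and Height measured at clinical patient visits during the follow up period", with blood pressure and laboratory values likewise from clinical visits. For the risk factors the SAP says "All blood pressure, A1c, and cholesterol test results were extracted similarly from the electronic health record". Weight has a richer record: "We also extracted the date and value for all body weight measures available from either the electronic health record or from eScale transmissions", over 15 months after randomization, with eScales given to all participants.

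For the 6-month weight the SAP gives a sequence: the EHR weight nearest 180 days within 6 +/- 3 months; failing that, half the change from baseline to an EHR weight at 12 +/- 3 months; failing that, an eScale weight at 6 +/- 3 months. If all are missing, "we assumed conservatively for the primary outcome analysis that the participant failed to reach the 5% weight loss threshold". The SAP does not make clear whether the steps before that last one also supply values for mean weight change.

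**The concern.** With no research visit, a blood pressure or laboratory value exists only if routine care produced one. A weight exists only if the patient attended or, where eScale values count, stepped on the scale. Either behaviour can be related to how the patient's weight is going.

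Availability can also differ by arm. Under Research Activity #3 both arms receive approaches 1 to 4, and only C3PO receives approach 5, targeted follow-up. The Protocol says that support is driven by the frequency and results of self-weighing. If eScale weights count as available, availability then depends on a behaviour that the added support targets.

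At stake are the preliminary effect sizes that the Protocol names as an aim of the Intervention Evaluation phase and means to use in designing a larger trial. Mean risk-factor changes are also among the SAP's key secondary outcomes. Small size does not explain the choice for weight: a likelihood-based mixed model needs no imputation step and uses data already extracted.

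**Working it through.** **Inputs.** From the documents: 40 patients per arm. The plan gives no missingness rate, SD, correlation or expected effect for these outcomes, so it has no figure to reproduce. Every other input below is an assumption.

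**Step 1: when does bias arise?** Let m be the fraction missing in an arm and d the mean among observed minus the mean among missing patients. The full mean is (1 - m) x observed + m x missing, so the observed mean is off by m x d. For the arm difference:

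bias = m_C x d_C - m_B x d_B (C = C3PO, B = Basic Resources and Services).

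In SD units, beside the 95% half-width 1.96 x sqrt(2/n):

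| Missing per arm | n per arm | Half-width | d = 0.5 in both arms | d = 0.5 in C3PO only | d = 0.5 and -0.5 |
|---|---|---|---|---|---|
| 20% | 32 | 0.49 | 0 | 0.10 | 0.20 |
| 30% | 28 | 0.52 | 0 | 0.15 | 0.30 |
| 40% | 24 | 0.57 | 0 | 0.20 | 0.40 |

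Equal rates with equal selection give no bias. Selection in one arm only gives 20% (0.10/0.49) to 35% (0.20/0.57) of the half-width. With no missing values the half-width is 0.44 SD.

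**Step 2: simulation with no true difference.** 4,000 trials per case, 40 per arm, SD of weight change 5 percentage points, correlation 0.8 between an earlier and the 6-month value, about 30% missing unless shown. The second estimate also uses the earlier value, which every patient has.

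| Missingness | Bias, available cases | Bias, earlier value used | t-test type I error |
|---|---|---|---|
| Completely at random | 0.01 | 0.00 | 0.050 |
| Same dependence on earlier value, equal rates | 0.00 | 0.00 | 0.053 |
| Same dependence, 78% vs 55% observed | 0.60 | 0.01 | 0.073 |
| Dependence in C3PO only | -0.81 | 0.01 | 0.094 |
| Opposite dependence in the two arms | -1.62 | 0.00 | 0.224 |
| C3PO only, on the unseen 6-month value | -1.05 | -0.44 | 0.126 |

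Under completely random missingness the SD of the estimate fell from 1.33 to 1.20, about 10%.

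**Step 3: simulation with a true difference of 2.0 kg.** SD 5 kg, correlation 0.8, missingness more likely after poor early loss. With missing rates 20 points apart, available-case bias was 0.24 to 0.66 kg, in either direction (0.24/2.0 = 12% to 0.66/2.0 = 33%). Using the earlier weight left about 0.05 kg or less. With equal rates of 30 to 50%, average bias was near zero and the standard error was 4 to 15% smaller.

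**Step 4: scale.** For 20% vs 40% missing the half-width is 1.96 x 5 x sqrt(1/32 + 1/24) = 2.65 kg; for 30% vs 50% it is 1.96 x 5 x sqrt(1/28 + 1/20) = 2.87 kg. So 0.24 to 0.66 kg is roughly 8% (0.24/2.87) to 25% (0.66/2.65) of the half-width.

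**The case against.** A reader might infer that the rule drops every patient without a clinic weight and ignores the 12-month and eScale data. The documents do not establish that. Among the fallback steps only the last, counting as failure, is expressly tied to the primary outcome analysis. The available-case sentence disclaims only advanced imputation, so the simpler steps may feed mean weight change too. Baseline enters every change score, and ANCOVA is specified. This part of the objection stands: for weight the text is ambiguous.

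The simulations also flatter the remedy. An EHR weight at 3 months already lies inside the 6 +/- 3 month window, so an earlier weight at that point is not clearly unused information. An always-observed earlier weight correlated 0.8 with the outcome has no support in the documents. In a rerun at 30% vs 50% missing, the remedy left about 0.16 to 0.35 kg of bias when missingness depended on the 6-month value itself. It gained nothing when missing patients had no earlier weight. Self-weighing times may be informative, and a constant data-source term does not correct for that.

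Nor do the documents support a 20-point gap between arms. Approach 5 works mainly through MyChart messages and telephone, which produce no clinic blood pressure or laboratory result. For those outcomes repeat values may be sparse, and with a baseline and one follow-up value a mixed model is close to available-case ANCOVA. No gain is shown there.

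Finally, this is a disclosed simplification for non-primary outcomes in a pilot without a power calculation. That limits the weight of the point. It does not supply the missing information on availability, or a reason to leave repeated weights out of a longitudinal analysis.

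**Conclusion.** The point holds as a risk that the plan neither examines nor reduces. Restricting mean changes to patients with a value can bias the between-arm difference, because availability can relate to weight progress and C3PO alone adds follow-up linked to it.

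Its size is unknown. The 0.24 to 0.66 kg illustration rests on the assumed 20-point gap, the 5 kg SD and the always-observed earlier weight. With equal missing fractions and equal selection in both arms, the bias is zero. A reader might infer that the reported mean differences are biased, or that the primary result is compromised. Neither follows: no missingness rates are given, and the binary primary analysis keeps every randomized patient by counting those with no usable weight as failures. That the two analyses cover different patients is not itself a defect.

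The change is worth making because it is cheap and serves the stated aim of preliminary effect sizes. The case is strongest for body weight.

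**What to change.** - **Body weight.** Estimate the arm difference at 6 and 12 months, with 95% CI, from a linear mixed model (arm by time, baseline weight included) on all dated EHR and eScale weights already extracted, with a term for data source. Report the available-case t-test alongside it.
- **Fallback steps.** State whether the 12-month and eScale steps feed mean weight change or serve the primary outcome only.
- **Blood pressure, A1c, cholesterol.** Keep the available-case set, but make ANCOVA adjusted for the baseline value the reported contrast. Use the longitudinal model only where repeat values exist.
- **Every continuous outcome.** Report by arm how many patients have a value, and the baseline characteristics of those with and without one.

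The cost is SAP wording and some extra programming, with no new patients, visits or data. The model assumes values are missing at random given the recorded weights. It reduces but does not remove bias if missingness or the timing of self-weighing depends on unseen weight, which is why the t-test and the availability tables should be reported with it.

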Because the proposed trial is a pilot and feasibility study, we have chosen a sample size needed to design the intervention to be implemented and sustained within routine practice workflows and to be usable to patients. Primary care practices in the Northwestern Medical Group (NMG) central region deliver care to more about 183,000 unique adult patients annually. Our pilot study will take place at the Galter Primary Care (GPC) site, which is relatively close to the medical campus and sees a patient case mix that mirrors the larger NMG patient population. About 70% of GPC patients have used MyChart in the past year, and 32% of those (N=5,967) meet the study's eligibility criteria. Thus, recruitment of the proposed sample will be feasible.

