## Analysis Plan

**Data Sources & Collection:** The primary outcome of interest was the percent of eligible patients who commit to a weight goal and reach 5% or greater weight loss at 6 months. Key secondary outcomes include the percent of eligible patients who set a weight goal (regardless of weight loss), and mean changes in pragmatically collected cardiometabolic risk factors. As a feasibility study, we also estimated costs per person per year for intervention delivery.

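### The continuous outcomes get both an unadjusted t-test on change and an ANCOVA with unnamed covariates, and the SAP does not say which estimate carries the treatment effect

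*SAP*

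**What the plan says.** The Statistical Analysis paragraph of the SAP gives two analyses for the same continuous outcomes.

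- First, the comparison between arms: "We conducted t-tests to compare all patients with available outcome measures in each study arm". The variables listed are "mean changes in body weight, systolic blood pressure, hemoglobin A1c, total cholesterol, and non-HDL cholesterol".
- Second, the adjusted analysis: "Multivariate models (ANCOVA and multivariate logistic regression) were used to estimate adjusted means (continuous variables) or proportions (categorical variables) for each pre-specified outcome".

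No covariate is named for the ANCOVA, so it is not stated that the baseline value of the outcome is one. Neither analysis is called lead, primary or supportive. Data Sources & Collection adds that for mean change "we analyzed only those patients with available outcome measures and did not use advanced imputation approaches for replacing missing values". The same section ranks "mean changes in pragmatically collected cardiometabolic risk factors" among the key secondary outcomes; the primary outcome is binary.

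The protocol (Study Activities, Phase 2) assigns 40 patients to each randomized arm and does not mention either analysis. The SAP text ahead of the Analysis Plan heading was not available for this check.

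**The concern.** A t-test on change subtracts the whole baseline value, which amounts to fixing the slope of follow-up on baseline at 1. When the true slope is below 1, as for measures that regress to the mean, this over-corrects. In a given trial, the arm that happens to start higher then tends to show the larger fall. ANCOVA with the baseline value as a covariate estimates the slope and removes that dependence, usually with a smaller standard error.

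What is at stake is the quality of the preliminary effect sizes, which the protocol lists as an aim of the pilot (Intervention Evaluation Phase, objective 1). With small arms and available-case data, the two analyses can give visibly different estimates for the same outcome. A reader of the SAP cannot tell which one is meant to inform the next trial, or what the adjusted one is adjusted for.

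**Working it through.** The plan states no SD, correlation, alpha or power for these outcomes, so it offers no figure to reproduce. The protocol says of its sample size: "Because the proposed trial is a pilot and feasibility study, we have chosen a sample size needed to design the intervention".

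**Inputs**
- Patients per arm: n = 40 (protocol, Phase 2). This is a ceiling, because only patients with measurements are analysed. n = 20 is an assumed low case.
- Correlation of baseline with follow-up, rho: not given; 0.3 to 0.95 assumed.
- SD: set to 1 and assumed equal at baseline and follow-up.
- The ANCOVA is assumed to include the baseline value of the outcome. The SAP does not say so.

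**Chance baseline difference.** Its standard error is √(2/n) = √(2/40) = 0.22 SD.

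**Shift of the change-score estimate.** Given a baseline difference D, the expected shift is −(1 − rho) × D. At rho 0.5 and D = 0.22 this is −0.5 × 0.22 = −0.11 SD.

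**Precision**
- Change-score SE = √[2(1 − rho) × 2/n]. At rho 0.5: √(1 × 0.05) = 0.224.
- ANCOVA SE = √[(1 − rho²) × 2/n × f], where f = 1 + 1/(2n − 4) is the small-sample cost of estimating the slope. At n = 40, f = 1 + 1/76 = 1.013. At rho 0.5: √(0.75 × 0.05 × 1.013) = 0.195.
- Variance ratio, ANCOVA to change score = f × (1 + rho)/2. At rho 0.5: 1.013 × 0.75 = 0.76.

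| rho | SE change, n = 40 | SE ANCOVA, n = 40 | Variance ratio, n = 40 | Variance ratio, n = 20 | Size of shift for D = 0.22 SD |
|---|---|---|---|---|---|
| 0.3 | 0.265 | 0.215 | 0.66 | 0.67 | 0.15 |
| 0.5 | 0.224 | 0.195 | 0.76 | 0.77 | 0.11 |
| 0.7 | 0.173 | 0.161 | 0.86 | 0.87 | 0.07 |
| 0.9 | 0.100 | 0.098 | 0.96 | 0.98 | 0.02 |
| 0.95 | 0.071 | 0.070 | 0.99 | 1.00 | 0.01 |

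At rho 0.5 a one-SE imbalance moves the change-score estimate by 0.11/0.224, about half of its own standard error. The 95% half-width at n = 40 falls from 0.44 to 0.38 SD. A simulation under the null (40,000 trials per setting) gave variance ratios within 0.01 of those in the table.

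**The case against.** The strongest reply is that the better method is already in the plan. ANCOVA is specified for every pre-specified outcome, and an unadjusted test followed by an adjusted model is a common layout. The wording can even be read as a division of roles, with the t-test for comparison and ANCOVA for adjusted means. That is fair and narrows the point, but neither the roles nor the covariates are stated.

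Four stronger readings are tempting, and the documents do not support them.

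- *The t-test is biased.* It is not: over repeated randomizations with everyone measured, the change-score comparison is unbiased. The 0.11 SD shift is conditional on a one-SE chance imbalance at an assumed rho.
- *ANCOVA is always more efficient.* That holds in large samples. At 20 per arm and rho 0.95 the ratio is 0.975 × 37/36 = 1.002, so nothing is gained. Available-case analysis may bring the trial near that size.
- *Type I error is inflated.* The simulation gave 0.057 to 0.078 per outcome at a nominal 0.05 with 40 per arm, but only if whichever result is significant may be reported. Nothing in the SAP says that either result would be withheld.
- *The trial's conclusions are at risk.* The primary outcome is binary, and the only stated threshold for proceeding to a larger trial is intervention cost per person. Neither depends on these t-tests.

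There is also a fair warning about timing. The SAP is in the past tense, so the analyses may already be done. Choosing a lead analysis and dropping the other now would itself be a post hoc choice.

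**Conclusion.** The point holds in a limited form. The SAP compares the arms on continuous outcomes by unadjusted t-tests on change, adds ANCOVA with unstated covariates, and does not say which estimate is the treatment effect. ANCOVA adjusted for baseline is the better lead. At 40 per arm it has about 0.76 of the change-score variance at rho 0.5 and 0.86 at 0.7, and it removes a conditional shift of about 0.11 SD (rho 0.5) for a one-SE imbalance.

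These sizes rest on assumed correlations, equal SDs at both times, and a model that includes the baseline value. Where rho is very high, plausibly for body weight, the choice makes almost no difference. The consequence is limited to non-primary outcomes of a pilot. It is an improvement worth making, not a flaw that threatens the trial's main result.

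**What to change.** In the Statistical Analysis paragraph, for each continuous outcome:

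1. Name as lead analysis an ANCOVA of the follow-up value on arm plus the baseline value of that same outcome, reported as an adjusted difference with 95% CI.
2. List any other covariates, or state that there are none.
3. Label the t-test on change descriptive.
4. Date and disclose the change, say whether results were already known, and keep both results visible.

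The cost is wording, plus a refit if the ANCOVA already run did not include baseline. No new data are needed, because every change score already requires a baseline value.

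### Variation of the arm difference by age or sex is judged from stratified results alone, with no estimate of the difference between stratum effects

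*SAP*

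**What the plan says.** The Statistical Analysis paragraph of the SAP gives one sentence to effect modification: "We explored stratified analyses by age and by sex to understand if preliminary outcome differences appeared to vary with these biologic variables". It names no age cut-point, no within-stratum test and no rule for deciding that effects vary.

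The models in which an interaction term could sit are described for another purpose: "Multivariate models (ANCOVA and multivariate logistic regression) were used to estimate adjusted means (continuous variables) or proportions (categorical variables) for each pre-specified outcome". Neither document mentions an arm-by-age or arm-by-sex term, or an interval for the difference between stratum effects.

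The primary outcome is binary, "the percent of eligible patients who commit to a weight goal and reach 5% or greater weight loss at 6 months", and the SAP "conducted chi-square or Fisher exact tests to compare all patients randomized to intervention and control arms" on it. For mean changes, the SAP states that "we analyzed only those patients with available outcome measures". The protocol (Phase 2: Intervention Evaluation) randomises 80 patients, 40 to each arm, and its closing section explains the size by the pilot purpose: "Because the proposed trial is a pilot and feasibility study, we have chosen a sample size needed to design the intervention". No power, alpha, expected rate or standard deviation is given.

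**The concern.** The stated question is whether the difference between arms changes with age or sex. The quantity that answers it is the difference between the stratum effects, with its uncertainty. Two separate stratum results leave the reader to judge that difference by eye, without its standard error, which is larger than that of either stratum effect.

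Stratifying by age also implies cutting it into groups. Age is among the routine data items the protocol lists for the trial (Protected Health Information section), so it could enter a model as a continuous variable. With no cut-point stated, the apparent pattern may depend on where the cut is later made.

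At stake is a secondary message of the pilot: a sex or age difference could be reported when the data are compatible with the same effect throughout.

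**Working it through.** The plan states no figure for this analysis, so there is none to reproduce. The check asks how often two strata look different when the true effect is the same in both.

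**Inputs.** From the protocol: 40 per arm. Assumed: two equal strata, so 20 per arm per stratum; two-sided alpha of 0.05; 10% response in the control arm and 10% to 35% in the intervention arm, identical in both strata.

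**Gap between stratum risk differences (no tests involved).** The SD of the difference between two stratum risk differences is √{2[p₁(1−p₁)+p₂(1−p₂)]/20}.
- 30% v 10%: √{2(0.21+0.09)/20} = √0.03 = 0.173.
- 10% v 10%: √{2(0.09+0.09)/20} = √0.018 = 0.134.

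A gap of at least 15 points is at least 3 patients in 20. With a continuity correction the threshold is 2.5/20 = 0.125. The normal approximation then gives 2[1−Φ(0.125/0.173)] = 47% and 2[1−Φ(0.125/0.134)] = 35%. Exact binomial enumeration gives the same two figures.

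**If within-stratum tests were run and read as significant or not (an assumption; the SAP does not say so).** With per-stratum power P, exactly one stratum is significant with probability 2P(1−P). At 30% v 10%, exact power is 0.357 (uncorrected chi-square) and 0.242 (Fisher), which gives 2×0.357×0.643 = 46% and 2×0.242×0.758 = 37%. Over the assumed range:

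| True rates, both strata | Gap ≥15 points | One stratum significant, Fisher | One stratum significant, chi-square |
|---|---|---|---|
| 10% v 10% | 35% | 2% | 7% |
| 15% v 10% | 39% | 6% | 13% |
| 20% v 10% | 43% | 13% | 24% |
| 25% v 10% | 45% | 25% | 36% |
| 30% v 10% | 47% | 37% | 46% |
| 35% v 10% | 48% | 46% | 50% |

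**Continuous outcomes, on the same reading.** Take the standardised effect that 40 per arm would detect with 80% power: d = (1.96+0.842)×√(2/40) = 0.626. In a stratum the SE is √(2/20) = 0.316, so power is Φ(0.626/0.316−1.96) = 0.508 and discordance is 2×0.508×0.492 = 50%. For overall power of 30%, 50% and 90% it is 29%, 41% and 47%. Available-case analysis would make the strata smaller than 20 per arm.

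**What an interaction estimate can deliver.** For two equal strata its SE is √(4/20) = 0.447, against √(2/40) = 0.224 overall, a ratio of 2.0. Power for an interaction as large as d is Φ(0.626/0.447−1.96) = 29%. Reaching 80% would take about 4×80 = 320 patients. For the binary outcome at 30% v 10%, the 95% CI for the difference in risk differences is about ±1.96×0.173 = ±34 points.

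**Sparse cells.** At 30% v 10%, an arm-by-stratum cell has no events with probability 0.9²⁰ = 0.122 (control) or 0.7²⁰ = 0.001 (intervention). At least one of the four cells is empty in 1−[(1−0.122)(1−0.001)]² = 23% of trials. An ordinary logistic interaction then has no finite estimate. A Wald test on the difference in risk differences can still be computed; its simulated false-positive rate is about 6%.

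**The case against.** The SAP hedges with words such as explored, preliminary and appeared, the trial is a small pilot, and no primary or secondary conclusion depends on this sentence. That stands and limits the severity. It does not make side-by-side results an answer to the question posed.

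A reader might infer that chi-square, Fisher or t-tests would be repeated within strata, and that one significant stratum beside a non-significant one would count as effect modification. The documents do not support this. The tests are described for all randomised patients or all with available measures, and no threshold is stated for strata. The significance columns above are therefore conditional. They also depend on the rates: both arms receive the first four intervention approaches and differ only in the fifth (Research Activity #3), so a small effect is plausible, and at 15% v 10% the Fisher figure is only 6%. The gap between estimates needs no such assumption.

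A reader might also infer that an age or sex finding could steer who is enrolled in the later trial. No text says so. The only threshold the SAP gives for proceeding is cost per person.

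Finally, one more logistic term is not a full remedy, and its error rate should not be presumed to be exactly 5%. The empty-cell problem is real, and interaction power is low. Both objections stand and shape the fix.

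**Conclusion.** The point holds as a minor one. The plan asks whether arm differences vary by age or sex and offers only stratified results, without an estimate of the between-stratum difference. With about 20 per arm per stratum, stratum risk differences would lie 15 or more points apart in about 47% of trials under an identical 30% v 10% effect, and in about 35% with no effect. If significance within strata were the yardstick, which is not stated, exactly one stratum would be significant in about 2–46% of trials (Fisher) or 7–50% (chi-square), over rates from 10% v 10% to 35% v 10%.

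These figures rest on assumed rates, an equal split and two-sided 0.05. The primary comparison is unaffected.

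**What to change.** - **Continuous outcomes:** add arm-by-sex and arm-by-age terms, with age continuous, to the planned ANCOVA. Report each interaction estimate with a 95% CI.
- **Binary primary outcome:** report the between-sex difference in risk differences with a 95% CI, or use a penalized (Firth) logistic interaction. The latter also handles continuous age and copes with zero-event cells.
- **Presentation:** show stratum estimates with CIs and no within-stratum p-values. Label the result exploratory and imprecise, and do not read a non-significant interaction as evidence of a uniform effect.

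The cost is a few sentences in the SAP and a small amount of extra modelling, with no new data. If the analysis is already done, the same estimates can be computed from the existing data set. The downside is that the intervals will be wide and power low: about 29% for an interaction as large as an overall effect that the trial could detect with 80% power. The gain is in honest reporting, since the interval shows how little the pilot can say about variation.
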